10.9. SARS-CoV-2 Infection Related Signs and Symptoms

During screening, treatment period and EOT visit, the investigator or designee will perform a respiratory signs and symptoms assessment (including but not limited to the examination of ears, nose, throat, sinuses and lungs, and the assessment for potential complications of SARS-CoV-2 infection throughout the study) at each scheduled visit specified in [Appendix 1](#). During the follow-up period, patients will be asked if they have any SARS-CoV-2 infection related signs and symptoms by telephone calls. The results will be classified as either “Normal” or “Abnormal”.

A shift table from baseline visit to each scheduled post-baseline visit for each category, except for the follow-up period, will be summarized by treatment group. Individual SARS-CoV-2 infection related sign and symptoms will be presented in a data listing.

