In Study CT-P59 3.2 Part 1, the efficacy of the proposed clinical regimen (40 mg/kg) and a higher regimen (80 mg/kg) were evaluated in patients with mild to moderate COVID-19 and overall, the study provided evidence that CT-P59 is effective for the treatment of mild to moderate COVID-19 patients. In particular, a potential benefit was seen for the primary endpoint of proportion of patients with clinical symptom requiring hospitalization, oxygen therapy, or experiencing mortality due to SARS-CoV-2 infection up to Day 28, which is clinically meaningful and is considered as both an individual patient benefit and public health benefit. Clinical efficacy data did not show a dose-response relationship for CT-P59 treatment. Viral shedding results from Studies CT-P59 1.2 and CT-P59 3.2 Part 1 were also suggestive of a relatively flat dose-response relationship. In addition, clinical safety showed that treatment-emergent adverse events (TEAEs) were comparable across CT-P59 and Placebo treatment groups. The majority of TEAEs were mild to moderate in severity and most events were singular and without associated dose-dependence.

Pharmacodynamic/PK analyses support the 40 mg/kg dose of CT-P59. The serum concentration of CT-P59 in human lung tissues was estimated using antibody distribution coefficients. Shah and Betts found that typically the concentration of monoclonal antibody in lung is 15% (Shah *et al*, 2013). Based on this, the CT-P59 40 mg/kg dose is expected to achieve approximately 14.9 µg/mL (99.5 µg/mL x 0.15) of serum concentration in lung tissue at 28 days after study drug administration in mild to moderate COVID-19 patients. The estimated serum concentration is above the in vitro EC90 value (25.09 ng/mL) of viral neutralization.

In conclusion, based on the clinical data from Studies CT-P59 1.1, CT-P59 1.2 and CT-P59 3.2 Part 1, a single dose of 40 mg/kg is considered as the appropriate dosing regimen to treat patients with mild to moderate COVID-19 in Part 2 of Study CT-P59 3.2.

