3.1.3 Follow-Up Period (From End-of-Treatment Visit to Day 180)

For all patients including patients who withdraw prematurely after the study drug administration, each telephone call follow-up will occur biweekly from EOT visit up to Day 180. During the Follow-up Period, patients will be asked if they have any SARS-CoV-2 infection related signs and symptoms by telephone calls to capture the suspicious ADE occurrence.

4 Patient Selection and Withdrawal Criteria

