6.2.1.3 Reporting Adverse Events

All AEs reported or observed during the study (from signing of ICF to EOT) will be recorded on the AE page in the eCRF and source documents. Information to be collected includes drug treatment, dosage, action taken with study drug, event term, date/time of onset and end date, investigator-specified assessment of severity and relationship to study drug, seriousness of AE, any required treatment or evaluations, and outcome.

Adverse events resulting from concurrent illness, reactions to concurrent illnesses, or reactions to concurrent medications must also be reported. All AEs will be followed up to adequate resolution. Signs and symptoms of SARS-CoV-2 infection recorded in the patient diary throughout the study will not be reported as AEs. Further, worsening of SARS-CoV-2 infection which is considered as unrelated to the study drug will not be reported as an (S)AE.

Adverse events will be graded for severity according to [Common Terminology Criteria for Adverse Events \(CTCAE\) Version 5.0](#). The Medical Dictionary for Regulatory Activities (MedDRA) will be used to code all AEs.

Any medical condition which is present during Screening but does not deteriorate should not be reported as an AE. However, if it deteriorates at any time during the study, it should be recorded as an AE.

The investigator's assessment of an AE's relationship to study drug is part of the documentation process, but it is not a factor in determining what is or is not reported in the study. If there is any doubt as to whether a clinical observation is an AE, the event will be reported.

The severity and the relationship or association of the study drug in causing or contributing to the AE will be characterized as defined in [Section 6.2.1.6](#) and [Section 6.2.1.7](#), respectively.

After the EOT visit, serious adverse drug reactions will be reported to the sponsor, or its designee.

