7.8.4.7 SARS-CoV-2 Infection Related Signs and Symptoms

The SARS-CoV-2 infection related signs and symptoms will be assessed at each scheduled visit with those at baseline and the results will be summarized by the scheduled visit and by treatment group.

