4. INVESTIGATIONAL PLAN

4.1. Overall Study Design and Plan

Part 2 of this study is a phase 3, randomized, parallel-group, placebo-controlled, double-blind study to evaluate the efficacy, safety, virology of CT-P59 in combination with Standard of Care (SoC) (except potential antiviral drugs and/or possible anti-SARS-CoV-2 activity drugs) in outpatients with mild to moderate symptoms of SARS-CoV-2 infection, not requiring supplemental oxygen therapy. ‘Outpatient’ in this study includes patients visiting the study center, and patients confined in the study center or quarantine at home due to local regulation or at discretion of the investigator.

[figure not shown]
In Part 2, approximately 1300 patients will be randomly assigned in a 1:1 ratio to CT-P59

40 mg/kg or placebo.

The study will be unblinded to the predefined unblinded teams of sponsor and Contract Research Organization (CRO) for reporting purposes after completion of the Day 28 assessments of the last enrolled patient in Part 2. However, the treatment assignment will remain blinded to the investigators, all designated study staff (with the exception of the unblinded study pharmacists or unblinded staff designated to prepare the study drug for infusion), and patients until the final CSR is generated.

The overview of study design for Part 2 is illustrated in [Figure 1](#).

Figure 1. Schematic Diagram of Study Patients for Part 2

Note: In Part 2, patients with body weight at or above 200 kg will receive 8,000 mg of CT-P59 or matching volume of placebo.

1. Of 1300 patients in Part 2, 822 high-risk patients will be included based on the sample size calculation.

The study will comprise of 3 study periods (including Screening, Treatment Period and Follow-up Period). An End-of-Treatment (EOT) visit will occur on Day 90 and the total study duration is planned as 180 days for each patient. The overview of the study is presented in [Figure 3](#).

Screening (Day-7 to 1): Screening will take place between Days –7 and 1, prior to the study drug administration. No study procedures will be performed prior to informing the patient about the study and obtaining written informed consent form (ICF). It is critical that patients receive study drug no more than 7 days from the onset of symptoms.

[figure not shown]

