10.1. Adverse Events

An adverse event (AE) is defined as any untoward medical occurrence in any patient during the study which does not necessarily have to have a causal relationship with the study drug. AEs will be collected from the date of the patient signs on the ICF until the end of the patient's participation in the study. All AEs will be coded to SOC and PT using the MedDRA version 23.1 or higher, and will be graded for intensity according to the National Cancer Institute Common Terminology Criteria for Adverse Events (CTCAE) version 5.0. A treatment-emergent adverse event (TEAE) includes any untoward medical occurrence in a patient after administration of a study drug, which does not necessarily have to have a causal relationship with the study drug. This includes any occurrence that is new or aggravated in severity or frequency from the baseline condition. A TEAE can therefore be any unfavorable and unintended sign (including an abnormal laboratory finding), symptom, or disease temporally associated with the use of the product, whether or not related to the study drug.

For the purpose of inclusion in TEAE tables and categorization of treatment period or Follow-Up period, incomplete AE start and stop dates will be imputed as follows:

If the stop date of an AE is partial or missing, the following rules will be applied.

- Missing day (e.g. XXAUG2020): Assume the last day of the month. (e.g. 31AUG2020)
- Missing day and month (e.g. XXXXX2020): Assume December 31st. (e.g. 31DEC2020)
- Missing day, month and year (e.g. XXXXXXXXXX): Leave it as Missing.

If the start date of an AE is partial or missing the following rules will be applied. If the stop date of the AE is partial, imputed stop date will be used instead of reported stop date.

- If the day of an Adverse Event is missing (e.g. XXAUG2020), the month and year of the partial date will be compared to the date of the first exposure to study drug.
 - If the month and year are equal for both dates, the AE start date will be imputed as the earlier date of: (i) the date of the first exposure to study drug, and (ii) the stop date of the AE.
 - If the month and year are not equal, the AE start date will be imputed as the first day of the month (e.g. 01AUG2020).
- If the day and month is missing (e.g. XXXXX2020), the year of the partial date will be compared to the date of the first exposure to study drug.

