10.1.3. Serious Adverse Events

A SAE is defined as any event that results in death, is life threatening, requires inpatient hospitalization or prolongation of existing hospitalization, results in persistent or significant disability/incapacity, or is a congenital anomaly/birth defect. Important medical events that may not result in death, be life threatening, or require hospitalization may be considered an SAE when, based upon appropriate medical judgment, they may jeopardize the patient and may require medical or surgical intervention to prevent one of the outcomes listed in this definition.

Treatment-Emergent Serious Adverse Events (TESAEs) during Treatment Period will be summarized by treatment group, SOC, PT, relationship, intensity or serious criteria, displaying the number and percentage of patients with at least one TESAE using only the worst intensity recorded at each level of summarization. The total number of events and number of patients with at least one TESAE over all SOC's will also be displayed.

Serious criteria and SAE description will be presented in an additional information listing.

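### Symptom answers from the Day 90–180 calls, and serious reactions reported after Day 90, are listed but not tabulated by arm, and the SAP and protocol disagree on how long adverse events are collected

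*SAP*

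**What the plan says.** SAP 4.1 states that "An End-of-Treatment (EOT) visit will occur on Day 90 and the total study duration is planned as 180 days for each patient". After EOT, contact is by telephone every two weeks. Protocol 3.1.3 gives the purpose: "patients will be asked if they have any SARS-CoV-2 infection related signs and symptoms by telephone calls to capture the suspicious ADE occurrence".

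On analysis:
- Protocol 7.8.4.7 has signs and symptoms assessed at each scheduled visit against baseline, and "the results will be summarized by the scheduled visit and by treatment group". No period is left out.
- SAP 10.9 has a shift table from baseline that "for each category, except for the follow-up period, will be summarized by treatment group". Individual results go to a listing.
- SAP 10.1.3 says "Treatment-Emergent Serious Adverse Events (TESAEs) during Treatment Period will be summarized by treatment group". SAP 10.1.1 puts the same limit on the table of all treatment-emergent events.
- SAP 10.10 and protocol 7.8.4.8 give the number and percentage of patients with suspicious ADE by arm, with no period limit.
- SAP section 6 tabulates discontinuations in the Follow-Up Period by arm and primary reason. The reasons include adverse event and death.

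On collection:
- SAP 10.1 says "AEs will be collected from the date of the patient signs on the ICF until the end of the patient's participation in the study".
- Protocol 6.2.1.2 and SAP Appendix 1, footnote 24, run from consent to the last assessment date or the EOT visit.
- Protocol 6.2.1.3 runs from consent to EOT and adds: "After the EOT visit, serious adverse drug reactions will be reported to the sponsor, or its designee".

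**The concern.** The potential effect on ADE incidence is part of a stated secondary objective, and the Follow-up Period was added to look for it. The calls put the same question to every patient in both arms at the same intervals. If the answers are only listed, the plan makes no randomized comparison of them. They count by arm only when an investigator judges a case to be suspicious ADE and completes that page of the case report form.

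The protocol also asks for serious drug reactions after EOT, yet no by-arm adverse event table would include them.

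The conflicting windows create a third problem. Someone who takes SAP 10.1 at its word would read a short Follow-up listing as few events, when under the protocol rule most kinds of event were not collected at all.

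**Working it through.** The plan gives no figure to reproduce here. The check is a comparison of texts, plus simple arithmetic for scale.

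**1. Length of the period.** 180 − 90 = 90 days after EOT, and 90/180 = 50% of planned time. At one call per 14 days, 90/14 = 6.4, so about six calls per patient. With 650 patients per arm, 650 × 6 = 3,900 planned calls per arm if all complete. Appendix 1, footnotes 2 and 3, brings a patient who withdraws early back for EOT assessments at the next scheduled visit, with calls from EOT on. For such a patient the untabulated stretch may start before Day 90.

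**2. Symptoms: protocol against SAP.** The calls are scheduled: protocol Table 11-2 and SAP Appendix 1 have a telephone follow-up column with this assessment marked. They therefore fall under protocol 7.8.4.7. Protocol section 7 requires changes from its planned analyses to be documented in the SAP. SAP section 12 lists two changes, the wider infected set and the removal of phenotype. The exclusion in SAP 10.9 is not among them.

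**3. Which by-arm outputs reach the Follow-up Period.**

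| Output | Source | Follow-up included by arm? |
|---|---|---|
| Signs and symptoms | SAP 10.9 | No, listing only |
| All treatment-emergent events | SAP 10.1.1 | No |
| Serious treatment-emergent events | SAP 10.1.3 | No |
| Suspicious ADE | SAP 10.10 | Yes, but not split by period |
| Discontinuations by reason | SAP section 6 | Yes |

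SAP 10.1 assigns each adverse event a Treatment Period or Follow-Up Period flag. The derivation needed for a Follow-up table already exists, but for Follow-up events it feeds listings only.

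**4. Collection windows.** SAP 10.1 goes to the end of participation, which is Day 180 for a completer. Footnote 24 and protocol 6.2.1.2 stop at the last assessment date or EOT. Read alone, the last assessment date might be stretched to the final call. Protocol 6.2.1.3 rules that out by stopping at EOT and setting a separate, narrower rule afterwards. The SAP therefore disagrees with the protocol and with its own appendix.

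**5. Three late events traced through the plan.**
- *Serious event judged drug-related, after EOT.* It is reported to the sponsor and, if it reaches the study database, listed. It enters neither SAP 10.1.1 nor 10.1.3.
- *Serious event judged unrelated, after EOT.* It is not recorded under protocol 6.2.1.3. Under SAP 10.1 it is recorded and listed.
- *Symptoms of infection reported on a call.* They are listed, and counted by arm only if declared suspicious ADE. Protocol 6.2.1.3 keeps worsening infection judged unrelated out of adverse event reporting at any time, and disease status monitoring ends at EOT (protocol 6.1.2, SAP 9.5). The call answers are then the main systematic record of such an episode.

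**6. Would a sparse table be informative?** If no patient among 650 in an arm had a given event, the one-sided 95% upper limit on its rate would be 1 − 0.05^(1/650) = 0.46%, assuming complete follow-up. A listing supplies no such statement.

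**The case against.** The strongest defence is that the outcome these calls were designed to find is tabulated. A reader might infer from the exclusions that late harm has almost no by-arm summary, or that declared ADE is the only by-arm number for the period. The documents support neither. SAP 10.10 counts suspicious ADE by arm with no period limit, protocol 6.2.15 applies the ADE work-up in the Follow-up Period, and SAP section 6 gives discontinuations by arm, including those for adverse events and death. That defence stands for ADE. It does not cover patients who report symptoms or have a serious reaction, stay in the study and are not declared ADE.

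Second, until EOT the assessment is an examination of ear, nose, throat, sinuses and lungs, and afterwards it is a telephone question. A call cannot be placed in a shift table by examination category. This is right, and the calls should stay out of that table. SAP 10.9 nevertheless classes results as normal or abnormal, so a separate count of patients is straightforward.

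Third, if the protocol's window governs, little beyond serious drug reactions exists to tabulate after EOT, and sites follow the protocol rather than the SAP. This also stands. It shrinks the table without removing the need for it, and leaves the sentence in SAP 10.1 in need of correction.

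Two further inferences are tempting. One is that the Treatment Period limit on infusion-related reactions (SAP 10.1.5) or drug discontinuation (SAP 10.1.4) matters. After a single Day 1 infusion it hardly does. The other starts from the protocol's estimate of "14.9 µg/mL (99.5 µg/mL x 0.15) of serum concentration in lung tissue at 28 days after study drug administration" and argues that exposure, and so ADE risk, persists past Day 90. The documents state no half-life for that extrapolation and do not relate any concentration to ADE risk, so it adds nothing here.

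**Conclusion.** The point holds in a limited form. The Follow-up symptom answers are reduced to a listing, contrary to protocol 7.8.4.7 and without an entry in SAP section 12. Serious drug reactions reported after EOT enter no by-arm adverse event table. The SAP's collection window contradicts the protocol and its own appendix.

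These are stated exclusions, not missing detail. They concern half of planned follow-up, but only descriptive safety output in the final Part 2 report. The Day 28 report and the primary and key secondary tests are unaffected.

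The conclusion assumes that the call answers are recorded per patient, as the SAP 10.9 listing implies, and that post-EOT serious reactions reach the study database, as the Follow-Up flag in SAP 10.1 suggests. If those reactions go only to a separate safety database, the SAP should say so.

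**What to change.** - SAP 10.9: leave the examination shift table without the calls. Add a by-arm count and percentage of patients with at least one abnormal sign or symptom reported in the Follow-up Period.
- SAP 10.1.3: tabulate serious treatment-emergent events by arm for the Follow-up Period and for the whole study, using the existing period flag.
- SAP 10.10: state that the suspicious-ADE table runs to Day 180, and show it by period.
- Reconcile SAP 10.1 with protocol 6.2.1.2 and 6.2.1.3 and Appendix 1 footnote 24, so that one collection window is stated throughout.
- SAP section 12: list any departure from the protocol that is kept.

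The tables use data already planned, so no new collection is needed. The cost is two or three descriptive tables. Their content will be sparse and partly self-reported, and a footnote should say so.

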10.10. Potential Effects of the Incidence of Antibody-dependent Enhancement

A patient will be considered to possibly have antibody-dependent enhancement (ADE) if the date of occurrence of suspicious ADE is filled on the “ADE Occurrence” page of eCRF.

If a patient has suspicious ADE, additional evaluations (including nasopharyngeal swab test, patient diary, SARS-CoV-2 infection related signs and symptoms assessment, vital signs, 12-lead ECG and troponin test) will be performed at each scheduled visit specified in [Appendix 2](#). If symptoms have not resolved or have worsened until 7 days after the day of suspicious ADE occurrence, same procedure will be repeated from the beginning until

when the symptoms are resolved and/or no SARS-CoV-2 infection is confirmed by RT-PCR (local).

Suspicious ADE will be summarized by treatment group, displaying the number and percentage of patients. Individual date of occurrence of suspicious ADE will be presented in a data listing, and additional evaluations will be included in the corresponding assessment listings.

11. EXPLORATORY ANALYSIS

11.1. Virology and Serology Analysis

Exploratory virology (viral shedding based on RT-qPCR, genotyping and phenotyping of SARS-CoV-2 viral isolates, and viral serology for SARS-CoV-2 antibody) analysis will be conducted in the ITTI Set and listed ITT Set. Viral shedding will also be analyzed in the ITT Set.

11.1.1. Viral Shedding

For viral shedding in nasopharyngeal swab specimen based on RT-qPCR, the actual values and change from baseline for viral shedding, percentage of patients with positive/negative viral shedding, duration of viral shedding, and AUC of viral levels will be summarized by each treatment group at each scheduled visit using descriptive statistics (n, mean, SE, minimum, median and maximum) or frequency tables. Mean (\pm SE) viral load titer will be plotted for each scheduled time point in log scale. If EOT result is available and the result from patient whose viral titer result at Day 28 is greater than or equal to negative threshold, the result of EOT visit will be included in summary table (the actual values and change from baseline for viral shedding, percentage of patients with positive/negative viral shedding).

The following rules present how viral titers will be treated in descriptive summary and AUC calculation, and categorized to Positive or Negative. AUC will be displayed to two decimal places. The analysis will be based on the 2.33 log₁₀cp/mL. Additionally negative threshold for 3 and 4 log₁₀cp/mL will be also considered although 2.33 log₁₀cp/mL is used to determine the analysis set defined in [Section 5.4](#).

Table 5. Rules of Viral Titers

Reported Value	RT-qPCR	
	Treated as	Categorized as
\geq Negative threshold	Reported value	Positive
< Negative threshold	Negative threshold	Negative
Negative	Negative threshold	Negative

Abbreviations: RT-qPCR= reverse transcription-quantitative polymerase chain reaction.

Duration (days) of viral shedding will be calculated as (Date/Time of post-baseline last positive sample – Date/Time of study drug administration).

AUC of viral level is calculated from date/time of study drug administration to date/time of last measurable value of patients who have at least one post-baseline result using linear trapezoidal rule. Viral level at baseline will be considered as result at study drug administration.

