6.4 Virology and Serology Assessments

Viral shedding based on RT-qPCR or cell culture, genotyping and phenotyping of SARS-CoV-2 isolates will be performed using the nasopharyngeal swab samples for all patients.

Samples will be secured at the central laboratory for analysis and backup samples will be retained. Viral serology for SARS-CoV-2 antibody test with assays detecting serum antibodies against SARS-CoV-2 will also be performed locally using the serum samples (if the assay is available). The sample for virology and serology assessments will be collected for analysis at the time points specified in [Table 11-1](#) and [Table 11-2](#).

Details of biologic sampling time points and acceptable tolerance windows for virology assessments are described in [Table 6-2](#) and [Table 6-3](#).

Table 6-2 Nasopharyngeal Swab Sampling Time Points for Virology Assessment – Part 1

Day	Time point	Window
Day 1	Pre-dose	Pre-dose within the day
Day 2	24 hours after start of infusion	± 4 hours
Day 3	48 hours after start of infusion	
Day 4	72 hours after start of infusion	
Day 5	96 hours after start of infusion	
Day 6	120 hours after start of infusion	
Day 7	144 hours after start of infusion	
Day 10	216 hours after start of infusion	
Day 14	312 hours after start of infusion	± 1 day
Day 17	384 hours after start of infusion	
Day 21	480 hours after start of infusion	
Day 28*	648 hours after start of infusion	± 3 days

Abbreviation: RT-qPCR = reverse transcription quantitative polymerase chain reaction; SARS-CoV-2 = severe acute respiratory syndrome coronavirus 2

*If the RT-qPCR result on Day 28 shows positive of SARS-CoV-2 infection, additional viral shedding will be conducted on Day 90.

Table 6-3 Nasopharyngeal Swab Sampling Time Points for Virology Assessment – Part 2

Day	Time point	Window
Day 1	Pre-dose	Pre-dose within the day
Day 3	48 hours after start of infusion	± 4 hours
Day 7	144 hours after start of infusion	
Day 10	216 hours after start of infusion	
Day 14	312 hours after start of infusion	± 1 day
Day 21	480 hours after start of infusion	
Day 28*	648 hours after start of infusion	
		± 3 days

Abbreviation: RT-qPCR = reverse transcription quantitative polymerase chain reaction; SARS-CoV-2 = severe acute respiratory syndrome coronavirus 2

*If the RT-qPCR result on Day 28 shows positive of SARS-CoV-2 infection, additional viral shedding will be conducted on Day 90.

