5.4.3. Intent-to-Treat Infected Set

The ITTI Set is defined as all randomly assigned patients with confirmed SARS-CoV-2 infection by pre-infusion result (Day 1) of reverse transcription quantitative polymerase chain reaction (RT-qPCR) who receive a complete or partial dose of the study drug. The SARS-CoV-2 infection will be confirmed based on the negative threshold of 2.33 log₁₀cp/mL. If the pre-infusion result at Day 1 is confirmed negative or missing and the Day 2 or Day 3 result is confirmed positive, this patient will also be considered as confirmed SARS-CoV-2 infection. A patient will be considered to have received a study drug if the patient is recorded as ‘Yes’ on the “Study Drug Administration” page of the eCRF.

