5.5. Definition of Baseline

The baseline value will be considered to be the last non-missing value before the study drug administration. Post-baseline values will be considered to be all values collected after the study drug administration.

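### Duration of viral shedding (exploratory) has no value for baseline-positive patients whose post-dose swabs are all negative, and counts a positive last available swab as completed shedding

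*SAP*

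**What the plan says.** SAP 11.1.1 defines the measure in one line: "Duration (days) of viral shedding will be calculated as (Date/Time of post-baseline last positive sample", less the date/time of study drug administration. SAP 5.5 fixes the key term: "Post-baseline values will be considered to be all values collected after the study drug administration". The Day 1 pre-dose swab is therefore not post-baseline.

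The summary is descriptive: "duration of viral shedding, and AUC of viral levels will be summarized by each treatment group at each scheduled visit using descriptive statistics", listed as n, mean, SE, minimum, median and maximum, or frequency tables.

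The set is the ITTI set, built from "randomly assigned patients with confirmed SARS-CoV-2 infection by pre-infusion result (Day 1") who were dosed, and extended in SAP 5.4.3 to patients first positive on Day 2 or Day 3. SAP 11.1 adds: "Viral shedding will also be analyzed in the ITT Set". Three thresholds apply. The main one is 2.33 log10 cp/mL, and SAP 11.1.1 continues: "Additionally negative threshold for 3 and 4" log10 cp/mL, with set membership staying at 2.33.

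In Part 2 the first post-dose swab is on Day 3, "48 hours after start of infusion", followed by Days 7, 10, 14, 21 and 28 (Protocol Table 6-3). A footnote there adds: "If the RT-qPCR result on Day 28 shows positive of SARS-CoV-2 infection, additional viral shedding will be conducted on Day 90". SAP 11.1.1 brings that late result into the tables of values, changes and percentage positive or negative. It does not mention duration.

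No text gives a value for a patient without a post-baseline positive, or a censoring rule for a patient whose last swab is positive. Protocol 7.8.5.2 names duration without defining it, and SAP section 12 is silent.

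**The concern.** Two groups of patients are mishandled, and both are defined by an outcome after randomization.

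The first is the fastest clearers. A patient positive before the infusion and negative from Day 3 onward has complete data and the best result the measure can show, but the formula has no end date to use. In a table of n, mean and median, a missing value is simply left out. The better a treatment clears virus before the first post-dose swab, the more of its successes are lost from its own mean.

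The second is patients whose shedding was still under way when observation stopped. Their duration is known only to exceed the time of the last swab, yet that time is averaged in as if shedding had ended. This shortens durations most in the arm that clears more slowly.

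Both effects push the group means toward each other. At stake is a fair description of an antiviral effect in an exploratory table, and whether readers can compare that table across arms.

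**Working it through.** The documents give no figure for duration of shedding, so there is none to reproduce. The check applies the formula to single patients and then illustrates the size by simulation.

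**1. Formula applied to swab patterns.** Swab times are from Protocol Table 6-3: 48, 144, 216, 312, 480 and 648 h, which is 2, 6, 9, 13, 20 and 27 days after dosing.

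- Positive on Day 1, all post-dose swabs negative: no value.
- Positive on Day 3 only: 2 days.
- Positive on Days 3 and 7, then dropout: 6 days, counted as complete.
- Positive at every swab through Day 28: 27 days, counted as complete unless the Day 90 swab is used, which the SAP does not say.

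**2. Effect of the missing values.** If a share q has no value and the rest average m days, counting the missing patients as 0 gives a mean of (1 − q) × m. With m = 10, this is 9.5, 9.0, 8.0 and 7.0 days for q = 5%, 10%, 20% and 30%.

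**3. Illustrative simulation.** All clearance and dropout inputs are assumptions, not taken from the documents:

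- 400,000 patients per arm
- Weibull clearance times with shape 1.5
- median clearance, active vs placebo, of 4 vs 6, 6 vs 9 or 9 vs 12 days
- dropout of 0%, 5% or 10%, uniform over 27 days
- swabs at the Part 2 times, each read without error

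The share clear by the first swab has a closed form under these inputs, 1 − 0.5^((2/median)^1.5). It gives 21.7%, 12.5%, 7.0% and 4.6% for medians of 4, 6, 9 and 12 days, in line with the simulated 21.8%, 12.4–12.6%, 7.0–7.1% and 4.6% without dropout.

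Results with 10% dropout (active / placebo; differences come from unrounded means):

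| Medians (days) | No post-dose positive | Last swab positive | Mean by SAP formula | Difference | Mean with complete swabs, none positive = 0 | Difference | Loss |
|---|---|---|---|---|---|---|---|
| 4 / 6 | 21.6% / 12.5% | 1.6% / 2.6% | 3.85 / 5.78 | 1.93 | 3.05 / 5.13 | 2.09 | 0.16/2.09 = 7.7% |
| 6 / 9 | 12.4% / 7.0% | 2.7% / 6.5% | 5.79 / 8.61 | 2.82 | 5.15 / 8.20 | 3.05 | 0.23/3.05 = 7.5% |
| 9 / 12 | 7.0% / 4.6% | 6.3% / 13.6% | 8.62 / 11.19 | 2.57 | 8.21 / 11.02 | 2.81 | 0.24/2.81 = 8.5% |

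Patients without a value were always commoner in the faster arm, and positive last swabs always commoner in the slower arm. In the middle row, adding the zeros alone raises the difference from 2.82 to 2.94; complete swabs raise it to 3.05. The two mechanisms contribute about equally there (0.12 and 0.11 days).

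Without dropout, the difference falls from 2.10 to 1.99, 3.05 to 2.94 and 2.83 to 2.74, which is 5.2%, 3.6% and 3.2%.

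The reference column also stops at Day 28, so a patient positive at that swab counts as 27 days on both sides. The losses above therefore leave out any effect of stopping at Day 28.

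**The case against.** The strongest reply is that little depends on this table. Duration is exploratory, and no treatment difference, confidence interval or p-value is planned for it. A reader would have to subtract two group means to see any shrinkage. The printed n would partly reveal missing patients. The bias found runs toward understating an effect, not toward a false claim of benefit. All of this stands, and it limits the point to a minor one.

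The reply also has force on coverage. Time to negative conversion, a secondary endpoint in SAP 9.3, is restricted to patients positive at baseline or on Day 2/Day 3, uses Kaplan-Meier, and censors withdrawals. The early clearer is an event there, and also contributes to the percentage-negative and AUC summaries. But that endpoint measures the first sustained negative result, not the last positive one, and it also censors for rescue therapy and hospitalization. It does not correct the duration table.

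Three stronger readings are tempting, and the documents do not support them:

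- A reader might infer that the SAP excludes early clearers by rule. It does not say so. Exclusion is what a missing value produces in descriptive statistics; a programmer could enter 0, but nothing instructs it.
- A reader might infer that the efficacy conclusions are biased. Duration feeds no primary, key secondary or tested endpoint.
- A reader might infer that most of the difference could vanish. Suppose 25% vs 10% have no post-dose positive and true means are 8 and 10 days. The reported means become 8/0.75 = 10.67 and 10/0.90 = 11.11, and a 2-day gap falls to 0.4. Those inputs are invented and put almost the whole effect before the 48-hour swab. No document figure supports them.

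**Conclusion.** The point holds as a minor defect in an exploratory summary. As written, the duration formula yields no value for a baseline-positive patient with only negative post-dose swabs, and it treats a positive last available swab as the end of shedding. This is more than a missing detail, because the stated formula combined with plain descriptive statistics produces outcome-dependent missingness and uncensored durations.

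Under the assumed Weibull clearance times and 10% dropout, the difference in mean duration was understated by roughly 8%. The direction was the same in every scenario run. The size depends on how much virus clears before Day 3, on dropout and on the distribution chosen, none of which the documents give. At 3 and 4 log10 cp/mL more patients will have no post-dose positive, so the gap is likely to matter more there; this was not simulated.

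**What to change.** Replace the one-line definition in SAP 11.1.1 with these rules:

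- Compute duration among patients positive at baseline at the threshold in use (2.33, 3 or 4 log10 cp/mL) who have at least one post-dose swab. Set it to 0 if no post-dose swab is positive.
- Do not assign 0 to a patient with no post-dose swab. Clearance was not observed in that patient.
- Summarise by Kaplan-Meier, censoring at the last available swab when that swab is positive.
- State how the Day 90 swab enters for patients positive at Day 28, for example by censoring at Day 28 or treating the end of shedding as interval-censored. A negative Day 90 result should not turn Day 28 into a completed duration, because the two visits are 90 − 28 = 62 days apart.
- State whether patients who enter the ITTI set through a Day 2 or Day 3 positive are included.
- Report by arm the number with no post-dose positive and the number censored.

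The cost is a few SAP sentences and a little programming, since Kaplan-Meier is already planned for the time-to-event endpoints in SAP 9.2 and 9.3. The downside is some overlap with time to negative conversion. If that overlap is unwelcome, the definition of 0 and the counts by arm are the minimum worth keeping.
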